Patients will be allocated to one of three groups using a web-based randomization by the SC: ketorolac, methylprednisolone, or hyaluronic acid. Group assignments will be concealed in opaque sealed envelopes with a numerical code of consecutive numbers reflecting patient enrollment. Envelopes will be stored in a secure, locked desk in the UConn orthopaedic research office and only to be opened once a patient has been determined to be eligible for study inclusion and provided informed consent.

Once informed consent is obtained, a licensed provider who is not part of the data collection (to maintain blindness) will prepare and inject the study drug. The patient will receive one of three options: 2cc of ketorolac tromethamine (15mg/cc) in 5cc of 0.5% ropivacaine hydrochloride without epinephrine, 2 cc of methylprednisolone acetate (40mg/cc) in 5cc of 0.5% ropivacaine hydrochloride without epinephrine, or Hylan G-F 20 (Synvisc-One) injection. In the US, methylprednisolone acetate is the most commonly used intra-articular steroid.¹⁷

- *Intervention: Each patient will receive one of the following interventions:*

- 1) 2cc of ketorolac *tromethamine* (15mg/cc) in 5cc of 0.5% *ropivacaine hydrochloride* without epinephrine; OR
- 2) 2 cc of methylprednisolone acetate (40mg/cc) in 5cc of 0.5% *ropivacaine hydrochloride* without epinephrine; OR
- 3) Hylan G-F 20 (*Synvisc-One*) or available hyaluronic acid.

- *Blinding:*

Both the patient and the investigators will be blinded to the treatment used until after final follow-up. Patients will not be told which drug they received. The investigators will be blinded too because the injections will be performed by a licensed provider who is not part of the data collection. Only the study coordinator will know which drug was administered and will compile the data until the study is completed.

- *Data collection:*

Patients will be asked to complete VAS, WOMAC, Oxford Knee questionnaire and Koos, Jr. Knee Survey prior to knee injection. Follow-up length is 6 months.

▪ *Sample Size and Justification:*

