A sample size calculation was performed to determine the adequate number of patients needed per group. A difference of 2 points in pain on a visual analog scale (VAS) was selected as the threshold for a meaningful between group difference. A standard deviation of 2.0 points was assumed based on previous research comparing steroid to viscosupplementation for osteoarthritis of the knee. A sample size of 20 patients per group will provide 80% power (β of 0.20) to detect a 2-point difference at an α level of 0.05 among the 3 treatment groups in an omnibus one-way ANOVA. To account for post hoc comparisons, a second calculation was carried out using a Bonferroni correction. A sample size of 25 patients per group will provide 81% power (β of 0.20) to detect a 2-point difference between each group in post hoc testing. To verify the sample size calculation, a Monte Carlo program was used to simulate 1,000 ANOVAs using these estimates with a sample size of 25 per group. This analysis resulted in greater than 90% power for the omnibus one-way ANOVA and greater than 80% for post hoc testing of between group means.

Explain on what basis it is reasonable to assume that sample size will be obtained:

Knee OA is a very common musculoskeletal condition, accounting for a significant proportion of patients presenting to orthopaedic providers.

Subject Characteristics and Justifications:

- Age: 18 years or older
- Ethnicity: No restrictions.
- Gender: No restrictions.
- Vulnerable Populations: None will be included.

Inclusion Criteria:

Patients over the age of 18 who present with 1) symptomatic knee OA and radiographic evidence of joint space narrowing and 2) are interested in knee injections for pain relief.

Exclusion Criteria:

- Patients interested in bilateral knee injections,
- Prior injections into the same knee within the past 3 months,
- Pregnant and/or lactating women,
- Inflammatory joint disease including rheumatoid or psoriatic arthritis,
- Concurrent use of anti-rheumatic drugs,
- Allergy or hypersensitivity to the study medications,
- Patients on an active pain management contract,
- Inability to make own decisions regarding the informed consent,
- Inability to read and/or understand English,
- Patients who are unable to return for follow-up or be reached by phone
- Patients with insurance that requires pre-certification for any of the study drugs.

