Describe length of subject's participation in the study including number of visits, frequency of visits and length of visits:

Patients will be in the study for 6 months. This time period will encompass their initial visit at which point they will be enrolled in the study and receive the injection as well their follow up visits. Patients will be asked to return at 3 and 6 months for evaluation and data collection. These visits are considered routine practice at our institution. Patients may also be contacted via telephone or email for follow-up if necessary. Participation will be voluntary with no financial compensation.

Methods of Data Collection and Types of Data to be Collected:

Data will consist of demographic information (age, gender, body mass index, comorbidities, etc.), as well as previous treatment modalities. The primary outcome is a visual analogue scale (VAS) for pain. Secondary measures will include the Western Ontario and McMaster Universities Osteoarthritis Index (WOMAC), length of pain relief, patient satisfaction, non-routine visits due to inadequate pain relief or complications, and cost of intervention.

Methods of Data Analysis:

Results for continuous variables will be described using means, standard deviations, medians, and/or interquartile ranges. Categorical variables will be described using counts and percentages. Numerical variables will be compared between groups using Wilcoxon's rank-sum test or Welch's two sample t-test. Categorical variables will be compared between groups using Pearson's chi-squared test or Fisher's exact test. All analyses will be done using R software (R version 3.2.3 (2015-12-10), Vienna, Austria) assuming a 5% level of significance.

5. Timetable:

Expected start date: 1/1/18

General Time Table: 1 year

Expected Completion Date: 7/31/20

6. Budget/Resources:

We will be applying for Orthopaedic Research and Education Foundation Grant during the IRB review.

7. Dissemination:

We plan to disseminate the results of our research in the form of peer reviewed publication and presentation at specialty meetings.

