APPENDIX A INVESTIGATOR INITIATED PROTOCOL TEMPLATE

Additional Details Pertaining to Study Design for Clinical Trials

1. For a clinical trial (e.g. a Phase I, II or III study), the use of the intervention must be fully described e.g., the treatment regimen for use of drugs, placebo, medical device etc. Also include plans for receipt of test article, storage, dispensing and reconciliation.

Intervention: Each patient will receive one of the following interventions:

- 4) 2cc of ketorolac *tromethamine* (15mg/cc) in 5cc of 0.5% *ropivacaine hydrochloride* without epinephrine; OR
- 5) 2 cc of methylprednisolone acetate (40mg/cc) in 5cc of 0.5% *ropivacaine hydrochloride* without epinephrine; OR
- 6) Hylan G-F 20 (*Synvisc-One*) or available hyaluronic acid.

Drug storage: Pyxis machine.

2. Provide a description of known adverse events due to the intervention and the plan to deal with such adverse events (e.g. does reduction, removal of device, removal from trial.):

The drug doses to be administered follow the standard of care (see pharmacy approval letter). Perhaps the main potential adverse event is infection. Patients will be counseled on signs of infection as part of the standard risks/benefits routinely performed with knee injection with instructions to call the clinic or report to the emergency room should any issues arise following the injection.

3. Describe circumstances that may lead to a subject being removed from the trial by the PI, e.g. due to failure to follow study procedures, and the process for doing so:

Meeting any of the exclusion criteria during study participation or failure/refusal to complete follow-up questionnaires.

4. Describe any stopping rules for the study:

None. All study drugs are routinely used for symptomatic knee OA.

5. Additional Comments by PI.

None.

References:

3. Bone and Joint Initiative: The Burden of Musculoskeletal Diseases in the United States. <http://www.boneandjointburden.org/2014-report/ivh12/osteoarthritis-and-allied-disorders>. Last viewed on November 12, 2007..
4. Treatment of Osteoarthritis of the Knee, 2nd Edition. American Academy of Orthopaedic Surgeons. Rosemont, IL. 2013. .

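### Length of pain relief is censored at 6 months or last contact, but the only planned tests for numerical outcomes cannot use censored times

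*Combined protocol and SAP*

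**What the plan says.** All references are to the combined protocol and SAP.

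- Methods of Data Collection and Types of Data to be Collected (section 4): VAS pain is primary. The secondary measures include "length of pain relief, patient satisfaction, non-routine visits". When relief ends, its unit and how it is recorded are not defined.
- Data collection (section 4): "Follow-up length is 6 months".
- Length of subject's participation (section 4): "Patients will be asked to return at 3 and 6 months for evaluation and data collection". Unscheduled contact is also allowed: "Patients may also be contacted via telephone or email for follow-up if necessary".
- Methods of Data Analysis (section 4): "Numerical variables will be compared between groups using Wilcoxon's rank-sum test or Welch's two sample t-test", "assuming a 5% level of significance". No censoring or time-to-event method is named anywhere.
- Appendix A, item 3: a patient may be removed from the trial for "failure/refusal to complete follow-up questionnaires". What then happens to that patient's data is not stated, and no dropout rate is given.

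**The concern.** Length of relief is a time to an event, the return of pain. For a patient still relieved at 6 months, or last heard from at 3 months while still relieved, only a lower bound is known. The named tests need one complete number per patient. Following the rule as written therefore leaves two options: enter the cut-off time as if relief had ended then, or leave the patient out.

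A cut-off at 6 months is the same for every arm. A cut-off at last contact is not, if the arms lose different numbers of patients. In that case the recorded durations differ between arms for reasons unrelated to the drugs. How long one injection lasts is also a natural companion to the cost-effectiveness hypothesis, although the plan describes no analysis that joins the two.

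**Working it through.** **The plan's own figures.** None concerns length of relief. The sample size rests on VAS pain: "A difference of 2 points in pain on a visual analog scale (VAS) was selected as the threshold", with SD 2.0. A noncentral F calculation with means 0, 1 and 2 and 20 per group gives 79.3% power, which reproduces the stated 80%. At α = 0.05/3 and 25 per group a t-test gives 85.0%, so the stated 81% is conservative. Neither figure bears on this point; 25 per arm is carried forward.

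**Inputs.** From the protocol: 25 per arm, contacts at 3 and 6 months, 5% level. Assumed: two-sided tests, one pair of arms, exponential durations, and some patients lost after the 3-month visit.

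**Closed form.** With median m, θ = m/ln 2. The share still relieved at 6 months is 2^(−6/m): 35% for m = 4, 50% for m = 6, 59% for m = 8. The expected recorded duration with cut-off c is θ(1 − 2^(−c/m)):

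| Median | θ | c = 6 | c = 3 |
|---|---|---|---|
| 4 | 5.77 | 3.73 | 2.34 |
| 6 | 8.66 | 4.33 | 2.54 |
| 8 | 11.54 | 4.68 | 2.64 |

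- No true difference (both medians 6), 10% v 30% lost: spurious difference (0.30 − 0.10) × (4.33 − 2.54) = 0.36 months. At 10% v 40%: 0.30 × 1.79 = 0.54 months.
- Medians 4 v 8, complete follow-up: the difference within 6 months is 4.68 − 3.73 = 0.95 months.
- Same medians, 10% lost in the shorter-relief arm and 30% in the longer: (0.7 × 4.68 + 0.3 × 2.64) − (0.9 × 3.73 + 0.1 × 2.34) = 4.07 − 3.59 = 0.48 months.
- Loss reversed: (0.9 × 4.68 + 0.1 × 2.64) − (0.7 × 3.73 + 0.3 × 2.34) = 4.48 − 3.31 = 1.16 months, from unrounded values.

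So entering the cut-off time moves 0.95 down to 0.48 or up to 1.16, depending on which arm loses more.

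**Simulation.** Lost patients are cut at 3 months and the rest at 6. Welch and rank-sum are applied to the cut times, and log-rank to the censored times. Ranges cover separate sets of 3,000 to 5,000 runs.

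| Scenario | Welch / rank-sum | Log-rank |
|---|---|---|
| No difference, no loss | 4.3–4.4% | 4.8% |
| No difference, 10% v 20% lost | about 6% | – |
| No difference, 10% v 30% lost | about 10–11% | 5–7% |
| No difference, 10% v 40% lost | 15–16% | 5–7% |
| Medians 4 v 8, no loss | 35–40% | 41–43% |
| Medians 4 v 8, 20% lost in each arm | 29–33% | 39–40% |
| Medians 4 v 8, 10% v 30% lost, more in the longer-relief arm | 12–14% | 37–39% |
| Medians 4 v 8, loss reversed | 52–55% | 39–40% |

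**Dropping instead.** If all lost patients are dropped and loss is unrelated to relief, error is 4.6–5.4% at 10% v 30% or 40% loss. Power at 10% v 30% is 29% against 37% for log-rank.

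**A different loss pattern.** With loss spread uniformly over 0–6 months and both medians 6, 10% v 30% loss gives about 9% false positives and 0% v 40% gives 26–28%. With both medians 3 the figures are about 6% and 13%. Log-rank stays at 4.7–5.5%. If only those lost while still relieved are dropped, error is about 6–9%.

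**The case against.** The strongest reply is that the tests are not invalid as such. A 6-month limit common to all arms leaves the error rate near 5% and costs only a few points of power. Inflated error needs unequal loss, for which the documents give no figure. Patients are blinded, each has one treatment visit and the same follow-up schedule, people who cannot return or be reached by phone are excluded, and telephone or email contact can limit loss. Entering cut-off times as durations is inferred from the named tests and the plan's silence; Appendix A could as well lead to non-completers being dropped. All of this stands and limits the point. It does not supply a rule for patients whose relief has not ended when last seen, and the power cost under equal loss remains.

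Three stronger readings are tempting, and the documents do not support them.

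- **The tests shrink the difference.** With medians of 4 and 8 months the full mean difference is 4/ln 2 = 5.77 months, against 0.95 within 6 months. That gap comes from the length of follow-up, not from the tests. A mean restricted to 6 months, recommended below, targets the same 0.95.
- **The tests generally understate differences.** They reject too seldom when the longer-relief arm loses more patients, and too often when the other arm does.
- **Relief can be observed only at 3 and 6 months.** Those are the scheduled contacts, but others are allowed, and a patient can be asked when the pain came back.

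It is also fair to say that defining the outcome comes before choosing its test. The fix starts there.

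**Conclusion.** The point holds in a limited form. The only stated rule for numerical outcomes does not suit length of pain relief, because some durations will be known only as lower bounds. With complete follow-up the consequence is minor. With patients lost while still relieved, entering cut-off times costs roughly 6 to 11 points of power at equal 20% loss. At 10% against 30–40% loss it roughly doubles or triples the nominal 5% error, and it can push a real difference either way. Dropping everyone lost protects the error rate if loss is unrelated to relief, at the price of power.

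The sizes rest on exponential durations, the chosen medians and assumed loss rates; at 10% against 20% loss the error is only about 6%. Log-rank also needs loss to be unrelated to the return of pain within each arm, so it does not rescue the comparison if patients drop out because of how they feel. The outcome is secondary, and neither the primary VAS analysis nor the sample size is affected. A reader might infer that a false difference is to be expected in this trial; nothing in the documents shows that loss will differ between arms.

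**What to change.** In the analysis section, exempt this outcome from the Wilcoxon/Welch rule and state:

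- Length of pain relief is the time from injection to return of pain, with return of pain defined in advance. Its date is asked at the existing 3- and 6-month contacts.
- Patients still relieved are censored at last contact or at 6 months, whichever is earlier.
- Arms are compared by Kaplan-Meier curves and a log-rank test, or by an interval-censored version if only the interval between contacts is known.
- The mean restricted to 6 months and the proportion still relieved at 3 and 6 months are reported alongside, both estimated with censoring taken into account.
- Patients removed under Appendix A, item 3, contribute up to their last contact.
- The number lost while still relieved is reported by arm, so that the reader can judge whether loss was unequal.

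The cost is a few sentences, one dated question at contacts already planned, and a little more programming in R. No visit is added. The drawbacks are some reliance on recall and results that describe relief within 6 months only.

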Study Title: Efficacy and Cost-effectiveness of Intra-Articular Ketorolac Injection for Knee Osteoarthritis: A Randomized, Controlled, Double-Blinded Study

NCT: 03694821

Last IRB Approval Date: 6/25/2019

Study Protocol

1. Title of the Study

Efficacy and Cost-effectiveness of Intra-Articular Ketorolac Injection for Knee Osteoarthritis: A Randomized, Controlled, Double-Blinded Study

Principal Investigator's Name and Contact Information

[name]

Assistant Professor, Department of Orthopaedic Surgery

University of Connecticut Health Center

[name]

Study Personnel

[name] PT, DPT, MSCTR (Statistician)

[name], BS (Study Coordinator)

[name], MS (Study Coordinator)

2. **Background**

Osteoarthritis (OA) of the knee is a common debilitating disorder with tremendous socioeconomic impact.^{1,2} The estimated financial burden of OA, including healthcare expenses and loss of productivity, is in excess of \$140 billion annually.^{2,3} Nonoperative management emphasizing rehabilitation, weight loss, and nonsteroidal anti-inflammatory drugs (NSAIDs) is currently the first line treatment for symptomatic OA of the knee.⁴ Other interventions, such as intra-articular injections with either corticosteroids or viscosupplements, remain controversial with mixed results in the literature.⁵⁻⁸

There is limited information about NSAIDs injection for the treatment of knee OA. Given that OA involves inflammatory processes leading to cartilage degradation and pain,⁹ NSAIDs injection represents a promising modality allowing for higher local tissue concentration and potentially providing potent anti-inflammatory and analgesic effects. In the US, ketorolac is the only NSAID available in injectable form. The advantages of ketorolac injection are multifold: 1) it is a relatively inexpensive medication; 2) there is strong evidence to support NSAIDs use, administered orally or topically, in the treatment of knee OA;¹⁰ 3) injection may be associated with less risk of systemic side effects¹¹ especially in patients who cannot tolerate oral NSAIDs; 4) ketorolac can potentially avoid the complications associated with corticosteroids, such as joint infection, cartilage breakdown, and loss of cartilage elasticity^{9,12,13}; and 5) ketorolac eliminates the risk of acute inflammatory reactions or need for serial clinic visits associated with viscosupplementation, which is ranked as the second highest OA-related healthcare expenditure.¹⁴

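### Harm appears in only one outcome, a visit-based item shared with inadequate pain relief, so the plan as written yields no interpretable complication count by arm

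*Combined protocol and SAP*

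**What the plan says.** Section 4, Methods of Data Collection, sets the outcomes. On the primary it says: "The primary outcome is a visual analogue scale (VAS) for pain". The secondary measures are WOMAC, length of pain relief, patient satisfaction, "non-routine visits due to inadequate pain relief or complications", and cost of intervention. The Data collection paragraph earlier in section 4 adds the Oxford Knee questionnaire and the KOOS, JR. before injection. Only the visit item mentions harm.

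On follow-up, section 4 says: "Patients will be asked to return at 3 and 6 months for evaluation and data collection". Telephone or email contact may be used if necessary. No adverse-event question is listed for any of these contacts.

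Appendix A, item 2, asks for known adverse events and the plan for dealing with them. The answer is "Perhaps the main potential adverse event is infection", and patients are counselled, with "instructions to call the clinic or report to the emergency room should any issues arise following the injection". It describes no definition, form, standard question, grading or tabulation by arm.

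The Background gives, among five advantages, that "ketorolac can potentially avoid the complications associated with corticosteroids, such as joint infection, cartilage breakdown, and loss of cartilage elasticity". It also says that ketorolac removes the risk of acute inflammatory reactions seen with viscosupplements. Methods of Data Analysis contains general between-group tests and no safety analysis.

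**The concern.** A return visit because the drug did not work and a return visit because it did harm are different events. The item joins them with a single *or*, and nothing in the plan asks for them to be reported apart. If an arm has fewer complications but more treatment failures, the two differences can offset each other in the between-arm comparison. If an arm is better on both, the total still does not show which cause produced the difference.

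Capture is the second problem. The measure is triggered by a visit, whereas Appendix A offers patients a telephone call as the first route. A problem dealt with by telephone is, on the plain words, not a visit. Whether an emergency room attendance is a non-routine visit for this purpose is not stated.

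At stake is whether the trial can report complications by arm in a form that a reader can interpret, when avoided complications are part of the stated rationale. The cost-effectiveness aim is touched too: contacts for failed relief and for complications may carry different costs, and contacts that are not recorded cannot enter any cost estimate meant to include them.

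**Working it through.** The plan states no complication rate, visit rate or safety power, so it has no figure to reproduce. The check has two parts.

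**1. Can a complication be counted from the plan as written?**

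| Route by which a complication comes to light | Where | Counted by a stated outcome? |
|---|---|---|
| Non-routine clinic visit | Section 4, secondary measures | Yes, but in an item shared with inadequate relief; no split by cause required |
| Emergency room or outside hospital | Appendix A, item 2 (emergency room only) | Not stated |
| Telephone call to the clinic | Appendix A, item 2 | No; it is not a visit |
| Mentioned at the 3- or 6-month visit | Section 4, length of participation | Could surface; no item records it |

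Only the first route leads to a stated outcome, and there the cause need not be reported.

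**2. What could be hidden, and what would separation gain?**

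Inputs: 25 patients per group (section 4, Sample Size and Justification); 5% significance level, taken as two-sided because the plan does not say; Fisher's exact test, one of the two tests named for categorical variables. All event rates below are assumptions.

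*Offsetting counts, one visit per patient.* Arm A: 6 relief + 1 complication = 7. Arm B: 3 relief + 4 complication = 7. Pooled: 7/25 = 28% in both, difference 0. Relief: (6 − 3)/25 = 12 percentage points. Complications: (1 − 4)/25 = −12 percentage points. These counts were chosen to cancel exactly.

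*Would separate tests detect it?* Fisher's two-sided p on the same counts is 0.35 for complications (1 against 4 of 25) and 0.46 for relief (6 against 3 of 25). Neither is close to 0.05.

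*Power over a range of assumed true rates.* Power is the sum, over all pairs (i, j) for which Fisher's p ≤ 0.05, of Bin(i; 25, p₁) × Bin(j; 25, p₂).

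| Arm A relief / complication | Arm B relief / complication | Pooled rate, both arms | Pooled test rejects | Complications alone |
|---|---|---|---|---|
| 24% / 4% | 12% / 16% | 28% | about 2% | about 11% |
| 20% / 4% | 4% / 20% | 24% | about 2% | about 23% |
| 36% / 4% | 4% / 36% | 40% | about 3% | about 78% |

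The pooled test cannot see the difference in any row. Testing complications alone has useful power only in the last row, which assumes a very large difference.

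*What a complication count by arm can say.* The chance of at least one case in an arm is 1 − (1 − p)²⁵: 22% at p = 1%, 40% at 2%, 72% at 5%. If no cases are seen, the one-sided 95% upper bound is 1 − 0.05^(1/25) = 11.3%. With so few events expected, one unrecorded complication can change what an arm's table shows.

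**The case against.** The strongest reply has five parts.

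- **Pooling is inferred.** The item names a type of visit and its two qualifying reasons. It does not call itself a composite or specify a pooled test, and the reason must be known for a visit to qualify. This stands in part: a single count is the natural reading, and a split may be possible from the same data, but the plan does not require it.
- **Complications could still be recorded.** A reader might infer that complications outside clinic visits are never counted. The documents do not support that. Scheduled visits are for evaluation and data collection, and complications could be raised there. What can be said is that no item records them.
- **Emergency visits may be included.** The wording is non-routine visits, not clinic visits. A reader might infer that emergency attendances are excluded, are the most easily missed, or are the costliest. The plan is silent on the first two and gives no figure for the third.
- **Efficacy has its own measures.** A reader might infer that equal visit counts would be taken for equal efficacy. VAS, WOMAC, length of pain relief and satisfaction address efficacy directly, so the residual problem concerns harm only.
- **Safety is not a tested hypothesis.** The stated aims are efficacy and cost-effectiveness, and the complication advantage is worded as a possibility. Nor would patient questions reveal cartilage breakdown or loss of elasticity. This stands, and it limits what the fix can deliver.

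The offsetting example is also constructed, and separate tests would have little power. Both points are accepted. None of this supplies the missing complication count.

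**Conclusion.** The point holds as a gap in outcome definition and capture. Followed as written, the plan yields no interpretable complication count by arm: its one harm-related item is triggered by visits, is shared with treatment failure, and is unclear about emergency and outside attendances, while complications settled by telephone fall outside it.

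Offsetting between arms is a possibility, not something the documents show; the example of 7 against 7 rests wholly on assumed counts. The loss is in descriptive safety reporting. It does not touch the primary VAS comparison, and separating the components would not turn this into a powered safety trial: about 11% power for an assumed 4% against 16%. The change is worth making because it costs little and affects a claim in the trial's own rationale.

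**What to change.** Replace the item with two secondary outcomes: (1) non-routine contacts for inadequate pain relief, and (2) complications. Then:

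- State that telephone, clinic, emergency room and outside-hospital contacts reported by the patient count.
- Ask every patient the same standard questions (event, date, reason) at the existing 3- and 6-month contacts, so that complications without a visit are also recorded.
- Have an investigator who is already blinded classify the reason. Section 4, Blinding, says that the study coordinator knows the drug given and compiles the data, so the coordinator should not assign the cause.
- Report both outcomes by arm, descriptively, with confidence intervals. The pooled count may be kept alongside.

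Cost: a change to the outcome list, a few questions on existing follow-up forms, and some investigator time to classify reasons. No added patients, visits or staff are needed. Relying on patient report avoids retrieving outside-hospital records, at the price of some recall error. Each component will have fewer events than the pooled count, so intervals will be wide. The change concerns measurement only and leaves clinical management as it is.

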
To date, there is a single published study on ketorolac vs. corticosteroid injection for knee OA, which showed similar pain relief but cost savings of 143% when using ketorolac.¹⁵ However, that study had only 35 patients with no power analysis. In addition, patients with no to minimal joint space narrowing or those with concomitant use of the study medications orally were not excluded. Most importantly, the corticosteroid used in that study has been voluntarily discontinued in the US market.

3. **Hypothesis, aims and objectives:**

- *Hypothesis:* Ketorolac injection is a cost-effective adjunct in the nonoperative treatment of knee osteoarthritis (OA) compared to steroids and viscosupplementation.
- *Aims/objectives:* The objective of this randomized, controlled, double-blinded, prospective study is to assess the efficacy and cost-effectiveness of knee injection with ketorolac in the nonsurgical

management of symptomatic OA compared to injections with corticosteroids and viscosupplements.

4. Study Design & Procedures:

Study Design: A prospective, randomized, controlled, double-blind trial.

- *Screening Procedures and who will perform them:*

Patients will be screened for eligibility when they present to the office for evaluation of knee pain. Screening will consist of a review of patients' medical history, physical exam, and X-rays which are routinely performed with or without being considered for a research study. If during the visit, a patient is interested in knee injections for symptomatic relief as part of conservative management, the patient will be informed of the possibility of participating in the research study and asked if there is interest in learning more. If the patient is interested, the investigators will make a note to the chart and let the patient know that the Study Coordinator (SC) will come by to present the details of the study, and inform the SC of the patient's interest. The SC will approach the patient at the end of the visit to provide an overview of the study and ask for verbal permission to review the patients chart to confirm eligibility. If found eligible, the SC will then proceed with a full consent process. Alternatively, if the patient prefers, a separate visit may be scheduled to conduct the consent process. Only study members will be allowed to obtain consent for study participation.

- *Randomization:*

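### The analysis section omits the ANOVA and Bonferroni step on which this three-arm trial was sized; followed as written, the family-wise error on the primary VAS is about 9–12%

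*Combined protocol and SAP*

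**What the plan says.** The Randomization paragraph in section 4 allocates patients to three arms: ketorolac, methylprednisolone or hyaluronic acid. Under Methods of Data Collection, "The primary outcome is a visual analogue scale (VAS) for pain"; no primary visit is named, and follow-up visits are at 3 and 6 months.

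Sample Size and Justification describes a two-stage procedure. Twenty patients per group are said to give 80% power at an α of 0.05 "among the 3 treatment groups in an omnibus one-way ANOVA". Then: "To account for post hoc comparisons, a second calculation was carried out using a Bonferroni correction". That second calculation gives 25 per group and 81% power "to detect a 2-point difference between each group in post hoc testing". A simulation check at 25 per group is reported as "greater than 80% for post hoc testing of between group means".

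Methods of Data Analysis gives a single rule for all numerical outcomes: "Numerical variables will be compared between groups using Wilcoxon's rank-sum test or Welch's two sample t-test", with all analyses in R "assuming a 5% level of significance". It names no omnibus test, no multiplicity adjustment and no single primary comparison. VAS has no separate analysis paragraph.

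**The concern.** Wilcoxon's rank-sum test and Welch's t-test each compare two groups, so an analyst with three arms must run several. The objective in section 3 sets ketorolac against two treatments ("compared to injections with corticosteroids and viscosupplements"), which implies two tests. The sizing wording implies all three pairs. Either way, 5% per test is not 5% for the primary outcome.

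The two sections can give opposite answers from the same data. Take one pairwise VAS comparison with p = 0.03. Under Methods of Data Analysis it is significant. Under a Bonferroni level of 0.05/3 = 0.0167 it is not. An analyst reporting it as positive would be following the protocol, and a chance difference between active treatments could become the trial's main claim.

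**Working it through.** **Inputs.** From the protocol: three arms; 25 per group; SD 2.0; difference 2 points; 5% level. Assumed: two-sided tests; normal data; equal arms; no dropout (the protocol gives no allowance); one VAS visit. The protocol does not give the Bonferroni divisor. I take 3, because the sizing refers to differences between each group and three arms make three pairs.

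**1. The plan's own sizing.**

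- *Omnibus test, 20 per group.* With means 0, 1, 2, the noncentrality is n·Σ(μᵢ − μ̄)²/σ² = 20 × (1 + 0 + 1)/4 = 10 on (2, 57) degrees of freedom. Power is 79.3%, against the stated 80%. This reproduces.
- *Pairwise test, 25 per group, at 0.0167.* The noncentrality is δ/(σ√(2/n)) = 2/(2 × √(2/25)) = 3.54 on 48 degrees of freedom. Power is 85.0%, against the stated 81%. The smallest n giving 81% is 23 per group. The stated 25 is therefore slightly conservative if the divisor is 3; 81% at 25 per group would correspond to a level of about 0.011.

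**2. Family-wise error, no true differences.** Simulation of 200,000 trials, 25 per arm, SD 2, exact Wilcoxon p-values, Monte Carlo standard error at most 0.07 percentage points:

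| Procedure | Welch | Wilcoxon |
|---|---|---|
| As written: any of 3 pairs at 0.05 | 12.1% | 12.0% |
| As written: either ketorolac pair at 0.05 | 9.0% | 8.9% |
| Any of 3 pairs at 0.05/3, no ANOVA | 4.3% | 4.2% |
| ANOVA at 0.05, then any of 3 at 0.05/3 | 3.8% | 3.3% |
| Either ketorolac pair at 0.025, no ANOVA | 4.6% | 4.5% |
| ANOVA at 0.05, then either ketorolac pair at 0.025 | 3.4% | 3.1% |

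*Checks.* For three pooled-variance t-tests at 5%, the studentized range distribution (3 groups, 72 degrees of freedom, cut-off √2 × t₀.₉₇₅) gives 12.1%. Independent tests would give 1 − 0.95³ = 14.3% and 1 − 0.95² = 9.75%; the true figures are lower because the comparisons share arms. A smaller run (20,000 trials) with the normal-approximation Wilcoxon p-value gave 11.5% and 8.4%, so the Wilcoxon decimals depend on the version of the test.

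**3. If both visits were tested.** Unadjusted testing at 3 and 6 months would give about 13–18% for four ketorolac tests and 17–23% for all six, for an assumed within-patient correlation from 0.9 down to 0. These figures are outside the 9–12%, which covers one visit and one pre-chosen test.

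**4. Power for a 2-point pair, 25 per arm.** The ranges with the ANOVA gate cover means 0/0/2 and 0/1/2.

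| Level | t-test/Welch, no gate | Welch, gated | Wilcoxon, no gate | Wilcoxon, gated |
|---|---|---|---|---|
| 0.05/3 | 85.0% | 84–85% | about 83% | 82–83% |
| 0.025 | 88.5% | 86–88% | about 87% | 85–86% |

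**The case against.** The strongest reply is that the two paragraphs stand in the same section of one short protocol and should be read together: the sizing paragraph sets out the VAS procedure, and Methods of Data Analysis is a generic list whose two-sample tests serve as the post hoc step. On that reading the error is at or below about 5% and the defect is a missing cross-reference. The reading is possible. But the sizing paragraph reports power calculations and gives the analyst no instruction, while the paragraph that does instruct sets 5% for everything.

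Four narrower points:

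- *The 9–12% assumes all arms are equal.* This is correct. If one arm differs by 2 points and the other two are equal, only one true null remains and the false-positive rate is about 5%. Family-wise error is properly judged where all nulls hold, but the condition must be stated.
- *Bonferroni is not needed once the ANOVA gate is in place.* With three arms, a significant ANOVA followed by unadjusted 5% Welch tests holds the error at about 5%, with more power for a 2-point pair: about 92% against 85% (means 0/0/2), or 88% against 84% (0/1/2). This is a valid alternative. It still needs an omnibus test that the analysis section lacks, and it would drop the Bonferroni step named in the sizing.
- *The divisor of 3 is inferred.* This stands; the 85.0% against 81% mismatch shows that it cannot be confirmed.
- *An equal-variance ANOVA sits awkwardly before Welch or rank tests.* This is fair. Welch's ANOVA or Kruskal–Wallis would match them better, but the sizing names the one-way ANOVA.

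**Conclusion.** The concern holds and should be fixed before unblinding. The analysis section sets a rule for the primary outcome that cannot compare three arms in one test and leaves out the error control behind the choice of 25 per group. No other part of the protocol restores it. At one visit, with one test chosen in advance, 25 per arm, two-sided 5% tests and no true differences, the family-wise error is about 9% for the two ketorolac comparisons and 12% for all three pairs. The sizing procedure with an inferred divisor of 3 gives about 3–4%. The combined reading would remove the excess, but the protocol must say that it is the one intended.

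**What to change.** Add a paragraph on the primary outcome to Methods of Data Analysis, for example:

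> VAS pain at [one visit named in advance] is compared across the three arms by one-way ANOVA at the 5% level. If significant, the three pairwise differences are tested by [Welch's t-test or Wilcoxon's rank-sum test, one named in advance], each at 0.05/3 = 0.0167 (Bonferroni).

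The visit and the pairwise test are for the investigators to choose.

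If only the two ketorolac comparisons in the section 3 objective are intended, say so, test each at 0.05/2 = 0.025 without the ANOVA gate, and change Sample Size and Justification to match.

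Either version is a change of wording with no added patients. With 25 evaluable per arm, power for a 2-point pair stays above the 81% used for sizing. The cost of the three-pair version is relative to the gated, unadjusted alternative: about 4 to 7 percentage points of power. If the investigators prefer that alternative, both sections must state it.
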